1.0 Objectives

1.1 Purpose/ Objectives.

This pilot study will investigate the optimal subcutaneous dose and the therapeutic potential of unacylated ghrelin to improve peripheral artery disease (PAD)-related brachial artery flow mediated dilation and reduce inflammation.

Ghrelin is a peptide and hormone that is primarily produced by P/D1 cells of the gastric fundus and circulates in both acylated and unacylated forms. Acylated ghrelin acts on the Growth Hormone Secretagogue Receptor (GHSR), increasing growth hormone levels, appetite, and insulin resistance (1-4). Unacylated ghrelin was originally thought to be an inactive metabolite. However, recent evidence shows that unacylated ghrelin promotes skeletal muscle cell regeneration, improves mitochondrial function, and increases skeletal muscle capillary density (5-7). Unacylated ghrelin also improves brachial artery flow-mediated dilation in humans (8). Unacylated ghrelin has been studied in more than 70 healthy humans without adverse effects (4,8-14). Unacylated ghrelin does **not** act on GHSR and does not increase appetite, or cause insulin resistance (4,8-14). However, unacylated ghrelin has never been studied in people with PAD. In addition, unacylated ghrelin has never been administered in a subcutaneous form to humans.

The pilot GIFT Trial will obtain preliminary evidence to identify the optimal dose of subcutaneously administered unacylated ghrelin in people with PAD. The results of this pilot study may be used to design a randomized trial of unacylated ghrelin, in subsequent study, to improve functioning and prevent mobility loss in older people with PAD.

Specific Aim. Because subcutaneously administered unacylated ghrelin has not been studied in humans, we will establish the association of increasing doses of subcutaneous unacylated ghrelin with circulating levels of unacylated ghrelin and brachial artery flow-mediated dilation (FMD) and levels of circulating inflammatory biomarkers. To achieve this aim, six PAD participants age 55 and older will receive a single subcutaneous injection of unacylated ghrelin at doses of 10 ug/kg, 20 ug/kg, and 40 ug/kg, respectively, on three separate days at least one week apart. Unacylated ghrelin levels will be measured at baseline and at defined intervals after each subcutaneous injection (30 minutes, 60 minutes, 1.5 hours, 3 hours, 6 hours, 8 to 12 hours and 24 hours). Brachial artery FMD will be measured at baseline, before the unacylated ghrelin injection, approximately six to eight hours, and 24 hours after each unacylated ghrelin injection (8). Circulating levels of inflammatory biomarkers will be measured at baseline and at six hours, 8-12 hours, and 24 hours after the subcutaneous injection of unacylated ghrelin. The lowest dose of subcutaneously delivered unacylated ghrelin that maximizes brachial artery FMD, maximizes levels of unacylated ghrelin, and minimizes circulating levels of inflammatory biomarkers will be used in future study.

PROTOCOL TITLE: Unacylated Ghrelin to Improve Functioning in PAD: the GIFT Trial

Specific Aim 2. We will assess the safety of increasing doses of unacylated ghrelin in six patients with PAD age 55 and older.

1.2 *Hypotheses.*

We hypothesize that unacylated ghrelin, administered subcutaneously, will increase brachial artery flow-mediated dilation (FMD) and reduce circulating levels of inflammatory biomarkers and that higher doses of subcutaneously administered unacylated ghrelin will be associated with greater increases in brachial artery FMD and lower circulating levels of inflammatory biomarkers.

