9.0 Procedures Involved

9.1 Study design.

STUDY OVERVIEW. We will identify the lowest subcutaneous dose of unacylated ghrelin that maximizes brachial artery flow mediated dilation (FMD). These PAD participants will receive three different subcutaneous doses of unacylated ghrelin on three different days and will undergo measurement of unacylated ghrelin levels prior to the injection and at specified time intervals. Each dose will be separated by a wash-out period of \geq one week. Data will be obtained for all six participants at each dose before moving to the next dose. We will test doses of 10 ug/kg, 20 ug/kg, and 40 ug/kg of unacylated ghrelin on three separate days for each participant. These doses were selected based on published literature and the experience of our consultants [name], who has an ongoing study of intravenously administered unacylated ghrelin in healthy

PROTOCOL TITLE: Unacylated Ghrelin to Improve Functioning in PAD: the GIFT Trial

people (R01-DK097550) and [name], who has an ongoing study of subcutaneously administered acylated ghrelin in older frail people without PAD (R21-AG040488).

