Selecting the dose of unacylated ghrelin for future study. We will select the lowest subcutaneous dose of unacylated ghrelin that maximizes brachial artery FMD and minimizes circulating levels of oxidative stress. We will also use unacylated ghrelin levels to select the unacylated ghrelin dose. In selecting the dose, greater increases in brachial artery FMD and lower levels of oxidative stress will be prioritized over the level of unacylated ghrelin. For example, if the dose of 40 ug/kg results in substantially higher levels of unacylated ghrelin compared to the dose of 20 ug/kg, but improvement in brachial artery FMD is similar between the 20 ug/kg and the 40 ug/kg doses, then we will select a dose of 20 ug/kg for use in a possible future trial of unacylated ghrelin in PAD patients.

PROTOCOL TITLE: Unacylated Ghrelin to Improve Functioning in PAD: the GIFT Trial

9.2 Describe all research procedures.

Please see sections 7.0, 8.1, 8.2, and 9.1 above.

Ankle Brachial Index (ABI). After the participant rests supine for five minutes, the right brachial, dorsalis pedis (DP), posterior tibial (PT) and left DP, PT, and brachial artery pressures are measured using a hand-held Doppler probe. Pressures are measured twice. The ABI is calculated for each leg by dividing the average of the DP and PT pressures by the average brachial pressure.

Questionnaire Administration. Participants will be administered study questionnaires by a trained and certified health interviewer.

Brachial Artery Flow-Mediated Dilatation (FMD). Brachial artery imaging will be performed by a Registered Diagnostic Cardiac Sonographer according to established protocol (44,45). Changes in FMD will be read by [name] University of Wisconsin Atherosclerosis Imaging Research Program Core Laboratory by a single reader blinded to participant characteristics. We have more than a decade of experience working with [name] reading center (44,47,48). Measurement reproducibility in [name] laboratory has a median FMD difference of 0.02% (inter-quartile range: -0.03 to 0.04).

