14.0 Risks to Subjects*

Overview of the GIFT Trial and anticipated characteristics of study participants. Six participants with PAD age 55 and older will participate in a

PROTOCOL TITLE: Unacylated Ghrelin to Improve Functioning in PAD: the GIFT Trial

dose finding study, in which participants will receive three different doses of unacylated ghrelin (10 ug/kg, 20 ug/kg, and 40 ug/kg) on three different days. Each dose will be separated by at least one week. Based on our previous work involving older participants with PAD, we anticipate that the average age will be approximately 76 years, that at least 33% of participants will be minorities, and that approximately 50% will be women. For example, in our recently completed SILC randomized controlled clinical trial of exercise in patients with PAD participants included 52% women and 45% African-Americans (39). In general, older patients with PAD have a high prevalence of comorbid diseases, particularly coronary artery disease, cerebrovascular disease, diabetes mellitus, and pulmonary disease. Thus the patient population is likely to be of generally poorer health than that of older men and women without PAD in the general population. Inclusion and exclusion criteria are provided in section 3.2.

Sources of material. We will collect data on levels of circulating unacylated ghrelin at multiple defined time points within a 24-hour period after three increasing doses of subcutaneously injected unacylated ghrelin. We will also measure brachial artery flow-mediated dilation (FMD) at baseline and at six or 8-12 hours after each of the three doses of subcutaneously injected unacylated ghrelin. Information obtained from the levels of circulating unacylated ghrelin and the brachial artery FMD will be used to select the dose of subcutaneous unacylated ghrelin to use in future trials.

Potential Risks.

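### The Specific Aim makes the highest unacylated ghrelin level a co-equal condition for choosing the dose, which conflicts with the ranking and worked example in Section 9.1

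*Combined protocol and SAP*

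**What the plan says.** The protocol states how the dose will be chosen in four places.

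- **Section 1.1, Specific Aim.** "The lowest dose of subcutaneously delivered unacylated ghrelin that" meets three conditions goes forward. In full, it is the one that "maximizes brachial artery FMD, maximizes levels of unacylated ghrelin, and minimizes circulating levels of inflammatory biomarkers will be used in future study". No condition is ranked above another.
- **Section 9.1, study overview.** The target is the lowest dose that maximizes FMD. Ghrelin level and biomarkers are not part of this statement.
- **Section 9.1, paragraph on selecting the dose for future study.** "We will select the lowest subcutaneous dose of unacylated ghrelin that maximizes brachial artery FMD and minimizes circulating levels of oxidative stress". It adds: "We will also use unacylated ghrelin levels to select the unacylated ghrelin dose". It then sets a priority: "greater increases in brachial artery FMD and lower levels of oxidative stress will be prioritized over the level of unacylated ghrelin". The worked example supposes a case "if the dose of 40 ug/kg results in substantially higher levels of unacylated ghrelin compared to the dose of 20 ug/kg" while the FMD improvement is similar, and takes 20 ug/kg.
- **Section 14.0, sources of material.** "Information obtained from the levels of circulating unacylated ghrelin and the brachial artery FMD will be used to select the dose". No ranking is given and biomarkers are not mentioned.

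The doses are 10, 20 and 40 ug/kg, given in that order to the same six people. Section 1.1 states that the peptide has not been given subcutaneously to humans before. Section 11.1 plans simple statistics and no power calculation.

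**The concern.** Choosing a dose for later trials is a main purpose of this pilot. With six participants and only simple statistics planned, the written rule is the main protection against settling the dose after the data are seen.

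FMD and the biomarkers respond to the drug. The ghrelin level does not: the substance measured is the substance injected. Asking for the dose with the highest level therefore comes close to asking for the highest dose, whether or not the drug works. As a co-equal condition it pulls against the preference for the lowest dose. It can also make two sections of the same protocol give different answers from the same data.

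**Working it through.** The plan gives no figure to reproduce, so there are three checks: the rules applied to the protocol's own example, the level condition alone, and the joint rule.

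**1. The worked example under each rule.** Take the premise in Section 9.1: level clearly higher at 40 than at 20 ug/kg, FMD similar. Suppose also that the biomarkers are similar.

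- Specific Aim: 20 ug/kg does not maximize the level, so it fails. If FMD and biomarkers count as tied, 40 ug/kg is the dose left.
- Section 9.1, selection paragraph: 20 ug/kg, as the text states.
- Section 9.1, overview: FMD alone, so the higher level has no bearing.
- Section 14.0: undetermined, because level and FMD are named without a ranking.

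**2. How often the level is highest at 40 ug/kg.**

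*From the documents:* n = 6, all three doses in each person, each dose twice the one before.

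*Assumed, because no subcutaneous pharmacokinetics are available:* exposure proportional to dose^b, and lognormal within-person variation with coefficient of variation CV. The log-scale SD is s = √ln(1 + CV²). Differences between people cancel because everyone receives every dose.

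For 40 against 20 ug/kg,

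P(40 above 20) = Φ( b · ln 2 · √6 / (s · √2) ).

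Example with b = 1 and CV 100%: s = √ln 2 = 0.833, so the argument is 0.693 × 2.449 / (0.833 × 1.414) = 1.44 and Φ = 0.925. Requiring 40 ug/kg also to exceed 10 ug/kg lowers this to about 0.92.

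Probability that 40 ug/kg has the highest of the three geometric means:

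| Exposure | CV 30% | CV 50% | CV 80% | CV 100% |
|---|---|---|---|---|
| proportional (b = 1) | >99.9% | 99% | 96% | 92% |
| square root (b = 0.5) | 98% | 90% | 79% | 73% |
| b = 0.25 | 84% | 70% | 59% | 55% |
| full plateau (b = 0) | 33% | 33% | 33% | 33% |

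No entry depends on any effect on FMD or inflammation.

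**3. What the joint rule returns.** Take the level as always highest at 40 ug/kg. The Specific Aim then returns 40 ug/kg if FMD is also highest there, and otherwise no dose. Simulated with n = 6 and an assumed SD of FMD change of 1 to 3 percentage points, choosing strictly the highest mean:

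| True FMD pattern | Returns 40 ug/kg | Returns no dose |
|---|---|---|
| equal at all doses | about 33% | about 67% |
| 1 point higher at 20 ug/kg only | 4–21% | 79–96% |
| 1 point higher at both 20 and 40 ug/kg | 43–49% | 51–57% |

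The biomarker condition is left out of this check. Adding it can only make 40 ug/kg rarer and no dose more common. Neither 10 nor 20 ug/kg can be returned under any pattern.

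**The case against.** The strongest reply is that Section 9.1 already deals with this. Its paragraph devoted to selecting the dose ranks FMD and oxidative stress above level. It then works through the very case that causes concern and declines to follow the higher level. The overview in the same section uses FMD alone. That stands, and it largely neutralizes the level condition wherever Section 9.1 is followed. It does not remove the unranked rule in the Specific Aim, and nothing says which section governs.

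Several stronger readings are tempting, and the documents do not support them.

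- A reader might infer that the Specific Aim picks 40 ug/kg whatever the benefit. It does not. The conditions are joint, so when FMD or biomarkers are not best at 40 ug/kg the literal result is no dose.
- A reader might take the percentages in the first table as the chance that 40 ug/kg is selected. They describe the level condition alone.
- A reader might say that the answer is fixed before the first injection. Subcutaneous exposure is unknown, its relation to dose is itself an aim, and the level measure (peak, area under the curve or a time point) is not defined. With strong saturation the condition loses most of its pull.
- A reader might say that the condition contradicts the preference for the lowest dose. The lowest dose that maximizes something is coherent and would operate if levels reached a plateau. The condition makes the qualifier nearly idle, which is a weaker charge.
- A reader might find the same push in Section 14.0. That sentence neither asks for a maximum nor excludes other inputs.
- A reader might conclude that under Section 9.1 the level can never matter. That paragraph gives the level no direction, so it could still inform the choice, for example by showing poor absorption.

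**Conclusion.** The point holds as a conflict between stated decision rules for the pilot's main output. The Specific Aim gives ghrelin level equal standing with FMD and biomarkers; the selection paragraph in Section 9.1 puts it below FMD and oxidative stress. On the protocol's own example, the first excludes 20 ug/kg and the second selects it. That part needs no assumption beyond similar biomarkers.

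The statement that level nearly restates dose does rest on assumptions. It is close to certain with proportional exposure and moderate variability, weaker with square-root exposure, and fails at a full plateau. Where the level peaks at 40 ug/kg, the Specific Aim leaves only 40 ug/kg or no dose. Whether the final choice would be distorted depends on which section the investigators follow, which the documents leave open. Nothing here says which dose is right.

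**What to change.** State one selection rule and use it in Section 1.1, both places in Section 9.1, and Section 14.0.

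- In the Specific Aim, remove the maximal ghrelin level as a co-equal condition.
- Bring the Specific Aim and Section 14.0 into line with the priority already stated in Section 9.1. Make the overview there agree with the selection paragraph.
- Say what the ghrelin level is for: a supporting exposure measure, reported by dose as peak and baseline-subtracted area under the curve.
- Settle the biomarker wording at the same time. The Specific Aim refers to inflammatory biomarkers, the selection paragraph to oxidative stress.

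Deleting only the Section 9.1 sentence that says levels will be used would not be enough, because the ranking and the example that follow still refer to level. The cost is an edit to a few sentences. It needs no new data, visits or participants.

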2.0 Background

2.1 *Relevant experience.*

- A. Lower extremity peripheral artery disease (PAD) affects 10-15% of community dwelling men and women age 65 and older (15-17) and will be increasingly prevalent as the U.S. population survives longer with chronic disease. Our prior work demonstrates that men and women with PAD have greater functional impairment and more rapid functional decline than those without PAD (15,18-24). The functional impairment documented in PAD is associated with loss of independence, increased mortality, and poor quality of life (22,25-27). Recent evidence shows that chronic disability, such as that associated with PAD, accounts for more than half of United States health burden (28). Furthermore, therapeutic advances have not kept pace with the growing burden of disability from chronic disease (28). Only two medications, pentoxifylline and cilostazol, are FDA-approved for treating PAD-associated walking impairment. Of these, pentoxifylline is usually ineffective and benefits from cilostazol are modest (29-32). New therapies are urgently needed for patients with PAD. This pilot study will test the therapeutic potential of subcutaneously administered unacylated ghrelin and the optimal dose of subcutaneously administered unacylated ghrelin in patients with PAD.
- B. Calf skeletal muscle fibers in PAD are damaged. Electron microscopy demonstrates pathologic changes in myofibrils, mitochondria, nuclei, and sarcolemma of calf muscle myofibers in patients with PAD (33). In 34 participants with PAD and 21 without PAD who underwent calf muscle biopsy, PAD participants had 30% higher protein carbonyl content ($P < 0.001$) and 40% higher 4-hydroxy-2-nonenal (HNE) levels ($P < 0.001$), indicating higher calf muscle oxidative stress levels in the PAD participants (33). More severe calf muscle oxidative stress was associated with more severe myofiber damage and fewer myofibers (33). Unacylated ghrelin has the potential to promote healthy calf muscle fibers in patients with PAD.

PROTOCOL TITLE: Unacylated Ghrelin to Improve Functioning in PAD: the GIFT Trial

- C. Calf muscle mitochondria are damaged in PAD. Skeletal muscle mitochondria from PAD patients also demonstrate a quantitative mitochondrial dysfunction, with reduced energy production (34-36). One study used magnetic resonance spectroscopy to compare the efficiency of mitochondrial oxidative phosphorylation in 12 men with PAD and 14 without PAD who engaged in submaximal plantarflexion exercise. After submaximal exercise, and controlling for blood flow, the PAD participants had poorer phosphocreatine recovery (137 seconds \pm 41 vs. 44 seconds \pm 3, $P=0.02$) and poorer adenosine triphosphate (ATP) recovery (60 seconds \pm 10 vs. 29 seconds \pm 2, $P=0.02$) than patients without PAD (36). These and other results (34,35) demonstrate an intrinsic defect in calf muscle mitochondrial function in patients with PAD. Unacylated ghrelin has the potential to promote improved calf muscle mitochondrial function in patients with PAD.

2.2 *Significance of the research.*

- A. **Overview of ghrelin.** Ghrelin is a peptide and hormone that circulates in acylated and unacylated forms. Unlike acylated ghrelin (1,3), unacylated ghrelin does not bind to GHSR1a and does not increase appetite or cause insulin resistance (4,9,11). In studies of humans and animals, unacylated ghrelin improves endothelial function, regenerates skeletal muscle cells, improves mitochondrial function, and increases capillary density (37-42). In summary, unacylated ghrelin has therapeutic effects on skeletal muscle and the vasculature without promoting insulin resistance or weight gain.
- B. **In a mouse model of hind-limb ischemia, unacylated ghrelin increased skeletal muscle regeneration, angiogenesis, and limb strength.** Togliatto and colleagues induced hindlimb ischemia in 81 mice and randomized them to intra-peritoneal injections of unacylated ghrelin, acylated ghrelin, or saline for 21 days (37). Mice who received unacylated ghrelin had significantly more skeletal muscle satellite cells (measured by Pax7/MyoD markers), significantly more regenerating skeletal muscle fibers, and significantly better plantarflexion function in the ischemic limb than mice who received acylated ghrelin or saline. Mice who received unacylated ghrelin had greater increases in capillary density in the skeletal muscle of their ischemic limb, compared to the other two groups. Greater increases in satellite cell number in mice who received unacylated ghrelin were mediated by P38/MAPK activation (37), consistent with previous reports that satellite cell proliferation depends on P38/MAPK protein activation. If these actions occur in humans with PAD, results will have major therapeutic implications for PAD patients. The purpose of this pilot study is to preliminarily test whether subcutaneously administered unacylated ghrelin improves brachial artery FMD in patients with PAD and to identify the most optimal dose of subcutaneously administered unacylated ghrelin in patients with PAD.

[figure not shown]
PROTOCOL TITLE: Unacylated Ghrelin to Improve Functioning in PAD: the GIFT Trial

- C. **Unacylated ghrelin promotes myocyte regeneration via the p38 pathway.** In a separate *in vitro* study, unacylated ghrelin induced differentiation of proliferating skeletal myoblasts and promoted their fusion into multinucleated syncytia (7). A high affinity binding site for deacylated ghrelin was identified on C2C12 myoblasts that is distinct from the (GHSR)-1a receptor that causes insulin resistance and increased appetite (7). In summary, preliminary evidence from *in vitro* and animal studies supports our hypothesis that unacylated ghrelin may improve functioning by promoting myocyte regeneration and differentiation in calf skeletal muscle damaged by PAD-related ischemia-reperfusion injury.

Importance of the GIFT Study. Effective therapies are urgently needed to prevent mobility loss in older people with PAD. The GIFT Trial will provide evidence for the optimal dose of subcutaneous ghrelin, which can later be used to design a pilot trial of unacylated ghrelin in older people with PAD.

Our proposed work will also facilitate subsequent studies of unacylated ghrelin therapy administered in the outpatient setting to older people with chronic diseases.

